#### 5 OBJECTIVES AND PURPOSE

## **5.1 Primary Outcome**

Safety is the primary outcome for this clinical gene transfer trial. Stopping criteria are based on development of unacceptable toxicity defined as the occurrence of two or more unexpected Grade III or higher treatment-related toxicities.

## 5.2 Secondary Outcome

Secondary efficacy outcome measures: Muscle biopsy analysis for safety and dystrophin expression will be studied using multiple serial sections.

- a) Expression of dystrophin as demonstrated by immunofluorescent in staining with a dystrophin C-terminus antibody and the exon 1-encoded epitope antibody (Manex 1A) in muscle biopsy sections.
- b) Dystrophin protein expression quantified by western blot using a dystrophin C-terminus antibody and the exon 1-encoded epitope antibody (Manex 1A) and assessed by densitometry in muscle biopsy tissue.
- c) Percentage of exon 2 exclusion from the dystrophin mRNA transcript as measured by RT-PCR analysis.
- d) Transduction efficiency will be measured by qPCR of a U7-targeting sequence primer pair amplifying the DNA containing the U7snRNA, and expressed as vector genomes normalized to a single-copy genomic DNA control in each muscle sample.

For immunofluorescence, multiple serial sections will be studied. For each of these measures, statistical analysis based on differences between pre- and post-gene transfer muscle specimens will be analyzed using a paired t test (p < 0.05). Sections and western blots will be prepared by a single technician, who will blind the sample identifier; images will be obtained and expression assessed by another technician blinded to the sample time point. Quantification of immunofluorescent staining will be performed using a published protocol that has been used for comparisons between multiple labs with highly reproducible results, with the results

reported as membrane-localized dystrophin staining intensity relative to normal muscle sections. The muscle analysis of gene expression will occur without breaking the blind.

Splicing of exon 2 will be assessed by RT-PCR analysis, which will be performed under the same blinding regimen as used for protein expression studies. RT-PCR and data analysis will be performed under standardized protocols, resulting in quantification of unskipped (Dup2), wild-type (WT), and exon 2 deleted (Del2) transcripts. Notably, both WT and Del2 transcripts are therapeutic.

Transduction efficiency will be measured by qPCR of a U7-targeting sequence primer pair amplifying the DNA containing the U7snRNA, and expressed as vector genomes normalized to a single-copy genomic DNA control in each muscle sample.

## **5.3 Exploratory Outcomes**

Exploratory functional outcome measures will be performed on the schedule as described.

- A) Muscle Function at 6 and 12 months post gene transfer in comparison to baseline values as follows\$:
  - a) In subjects enrolling under at 36 months of age or younger:
    - Improvement or statistically significant stabilization of Bayley-IV scores (Bayley Scales of Infant and Toddler Development)
  - b) In subjects enrolling at greater than 36 months of age and younger than 5 years of age:
    - Improvement or statistically significant stabilization of the North Star Ambulatory Assessment (NSAA) score.
    - Time to climb 4 stairs
    - The amount of time required to walk 100 meters (100MWT)
  - c) In subjects enrolling at 5 years or greater, improvement or statistically significant of the following:
    - North Star Ambulatory Assessment (NSAA) score.
    - Time to climb 4 stairs
    - The amount of time required to walk 100 meters (100MWT)
    - The force generated in knee flexion and extension in the maximum voluntary isometric contraction (MVICT)
      - \$Subjects will be tested using age appropriate assessments.
- B) As an exploratory efficacy measure, muscle MRI will be assessed using T2-weighted multislice spin echo (SE) axial images and single voxel 1H-MRS from both the lower leg and thigh to measure lipid fraction and (1)H2O T2 signal. These will be performed at baseline and at 6, 12, 18 and 24 months post infusion, but only if sedation is not required. Data will be assessed using published techniques and compared to baseline values in collaboration with [name], University of Florida (see Section 10.2 for more details).
- C) As an exploratory efficacy measure, the percentage of exon 2 exclusion from the dystrophin mRNA transcript will be measured by RNA-Seq analysis.
- D) Additional analyses performed on muscle biopsy tissue will include:

- a) Immune staining at 90 and 180 days as well as 12 months will be performed on biopsy specimens for members of the dystrophin-associated protein complex, including the sarcoglycans and β-dystroglycan.
- b) Muscle morphometrics will also be performed, including fiber size histograms and quantification of central nucleation at 90 and 180 days as well as 12 months.

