Secondary Outcomes	We propose the following secondary efficacy outcome measures in	
Secondary Outcomes	leg muscles, each in comparison to baseline values:	
	Expression of dystrophin as demonstrated by	
	immunofluorescent staining with a dystrophin C-terminus	
	antibody and the exon-1 encoded epitope antibody (Manex	
	1A) in muscle biopsy sections.	
	
 
Dystrophin protein expression quantified by western blot
 
	
	using a dystrophin C-terminus antibody and the exon-1	
	encoded epitope antibody (Manex 1A) and assessed by	
	densitometry in muscle biopsy tissue.	
	Percentage of exon 2 exclusion from the dystrophin mRNA      Percentage of exon 2 exclusion from the dystrophin mRNA      Percentage of exon 2 exclusion from the dystrophin mRNA      Percentage of exon 2 exclusion from the dystrophin mRNA      Percentage of exon 2 exclusion from the dystrophin mRNA      Percentage of exon 2 exclusion from the dystrophin mRNA      Percentage of exon 2 exclusion from the dystrophin mRNA      Percentage of exon 2 exclusion from the dystrophin mRNA      Percentage of exon 2 exclusion from the dystrophin mRNA      Percentage of exon 2 exclusion from the dystrophin mRNA      Percentage of exon 2 exclusion from the dystrophin mRNA      Percentage of exclus	
	transcript as measured by RT-PCR analysis.	
	• Transduction efficiency will be measured by qPCR of a U7-	
	targeting sequence primer pair amplifying the DNA	
	containing the U7snRNA, and expressed as vector genomes	
	normalized to a single-copy genomic DNA control in each	
T. J	muscle sample.	
Exploratory	We propose the following exploratory clinical outcome measures,	
Outcomes	each in comparison to baseline values:	
	1) For Muscle Strength:	
	
 
In subjects enrolling at 36 months of age or younger:
 
	
	improvement or stabilization of Bayley-IV scores (Bayley	
	Scales of Infant and Toddler Development)	
	
 
In subjects enrolling at greater than 36 months of age but
 
	
	younger than 5 years: improvement or stabilization of the	
	North Star Ambulatory Assessment (NSAA) score, time to	
	climb four stairs and amount of time to walk 100 meters	
	(100MWT)	
	, , , , , , , , , , , , , , , , , , ,	
	• In subjects enrolling at age 5 years or greater: improvement or	
	statistically significant stabilization in:  o North Star Ambulatory Assessment (NSAA) score	
	 	
	Amount of time required to walk 100 meters (100MWT)      Time to climb four stoirs	

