## 4.3.3 Current Treatments for DMD

The only therapeutic approach that has clearly demonstrated unequivocal efficacy for treatment of DMD is glucocorticoids (prednisone or deflazacort). Treatment with one of these agents has been repeatedly shown to result in increased muscle strength and delayed loss of ambulation. Deflazacort has recently gained FDA approval for treatment of boys with DMD, based largely on a slightly more favorable side effect profile. However, treatment with either of these drugs can be associated with significant side effects, including weight gain, Cushingoid features, hypertension, cataract formation, loss of bone density, vertebral compression fractures, long bone fractures, and behavioral problems.

Molecular therapies, such a gene replacement, exon skipping, and nonsense mutation suppression provide a promising alternative to glucocorticoids. Exon skipping utilizes antisense oligomers to induce altered pre-mRNA splicing to restore an open reading frame, and eteplirsen has received FDA approval, based largely on a small but statistically significant increase in dystrophin expression. Nonsense suppression utilizes an oxadiazole to enable ribosomal readthrough of nonsense mutations to theoretically make full length dystrophin (PMID 28728956). However, both exon skipping and the as-yet unapproved nonsense suppression approach are only beneficial to small subsets of patients with specific mutations, 13% and 15% respectively.

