#### 7.1 Inclusion/Exclusion

Inclusion Criteria

- 1. Age greater than 6 months and less than 14 years.
- 2. Confirmed duplication of exon 2 the DMD gene using a clinically accepted technique that completely defines the mutation.
- 3. Pre-ambulant (not yet walking) or ambulant (as defined by the ability to walk 10 meters without assistance).
- 4. Males of any ethnic group will be eligible
- 5. Ability to cooperate with muscle testing.
- 6. In subjects age 4 and above, stable dose and regimen of corticosteroid therapy (including either prednisone or deflazacort and their generic forms) for at least 12 weeks prior to gene transfer.

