## 9.1 Study Visits

### 9.1.1 Screening (day -45 to day -1)

Informed consent will be obtained prior to the collection of any data and any study related procedures. Baseline measures from subjects will be obtained prior to gene transfer and will occur over two visits (up to 3 weeks apart). Because a pre-existing antibody response would be exclusionary, ELISA and ELISpot testing will be performed at the first visit, allowing the results to be reviewed prior to the open muscle biopsy and its subsequent risks (including sedation). The weight obtained at screening will be used to calculate the viral vector dose.

The following assessments will occur at these visits:

- Informed Consent
- Assent, if applicable
- Medical history
- Concomitant Medications
- Physical Exam
- Vital Signs (temperature, respiratory rate, heart rate, blood pressure, height (see Section 10.5 for more details), and weight)
- MRI of the lower legs (see Section 10.2 for more details)
- ECHO
- ECG
- Functional tests (variable depending on age of enrollment)
  - Enrollment age:  $\leq$  36 months
    - Bayley-IV scores (Bayley Scales of Infant and Toddler Development)
  - o Enrollment age: > 36 months and < 5 years of age
    - North Star Ambulatory Assessment (NSAA)

- Time to climb four stairs
- Amount of time required to walk 100 meters (100MWT)
- Enrollment age:  $\geq$  5 years old until Non-Ambulant
  - North Star Ambulatory Assessment (NSAA) score
  - Time to climb four stairs
  - Amount of time required to walk 100 meters (100MWT)
  - Force generated in knee flexion and extension in maximum voluntary isometric contraction (MVICT).
- Pulmonary functional tests (PFTs), including forced vital capacity. (See Section 10.3 for more details.)
- Open Muscle Biopsy (For details, see Section 10.2)

The following blood lab work will occur at this visit. (Lab work may be drawn over several days during visit if deemed necessary by study team except as noted above for ELISA and ELISpot.)

- Complete blood cell count (CBC) and differential, platelets
- Aspartate aminotransferase (AST)/alanine transaminase (ALT)
- Gamma-glutamyl transpeptidase (GGT)\*
- A Comprehensive Metabolic Panel (CMP) that includes:
  - Albumin/Serum total protein
  - Serum total bilirubin
  - Electrolytes
  - o Calcium
  - o Creatinine/Blood Urea Nitrogen (BUN)
  - Serum glucose
  - Alkaline phosphatase
- Prothrombin time (PT)/activated partial thromboplastin time (PTT)/INR
- Amylase
- Creatine kinase (CK)
- Cystatin C

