#### 9.1.2 Gene Transfer Visit

#### 9.1.2.1 Pre Infusion Visit (Day -1)

Subjects will arrive at the Nationwide Children's Hospital within 24 hours prior to gene transfer.

The following assessments will occur at this visit:

- Medical history
- Concomitant Medications
- Adverse Events
- Physical Exam
- Vital Signs (heart rate, respiratory rate, temperature, blood pressure, height (see Section 10.5 for more details) and weight)

The following blood lab work will occur at this visit:

- Complete blood cell count (CBC) and differential, platelets
- Aspartate aminotransferase (AST)/alanine transaminase (ALT)
- Gamma-glutamyl transpeptidase (GGT)\*
- A Comprehensive Metabolic Panel (CMP) that includes:
  - o Albumin/Serum total protein
  - o Serum total bilirubin
  - Electrolytes
  - o Calcium
  - o Creatinine/Blood Urea Nitrogen (BUN)
  - o Serum glucose
  - Alkaline phosphatase
- Prothrombin time (PT)/activated partial thromboplastin time (PTT)/INR
- Creatine kinase (CK)
- Direct Bilirubin
- ELISpots for T-cell responses to AAV9 and Dystrophin
- Whole blood for biobanking

In previous gene therapy studies at NCH, there has been an observed antigen specific T-cell response to the AAV vectors. This is an expected response between 2 - 4 weeks following gene transfer. One possible consequence to such antigen specific T-cell responses is clearance of the transduced cells and loss of transgene expression. All subjects (ages 4 years and older) will already be on prednisone, prednisolone, or deflazacort for 12 weeks at time of enrollment as part of the inclusion criteria. The standard clinical dose of prednisone or prednisolone is 0.75 mg/kg/day, and the standard clinical dose of deflazacort is 0.9 mg/kg/day. In order to dampen the host immune response to our AAV-based therapy, for each subject the glucocorticoid dose will be increased to prednisone or prednisolone 1.0 mg/kg/day, not to exceed 60 mg/day; subjects on deflazacort at enrollment will be placed on prednisone or prednisolone for the immediate perinijection period. For subjects younger than 4 years of age who may not be on a corticosteroid,

\* For subjects taking drugs that potentially induce GGT synthesis through the cytochrome P450 system, the clinically significant range will be estimated starting at two times the levels obtained from the baseline screening test and up.

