# 10.6.1 Prophylactic Administration of Prednisone/Prednisolone

All subjects will be discharged from the hospital on oral prednisone or prednisolone at 1 mg/kg/day, which will be adjusted according to IFN-gamma T-cell studies in the following weeks. Subjects will also continue on a PPI until they return to their baseline corticosteroid dose or sooner based on the subject's symptoms and discretion of the sponsor investigator and/or parent.

If the **30 day** post-infusion IFN-gamma T-cell responses to AAV9 and dystrophin show ≤50 SFC per 1 x 10^6 PBMCs, the subject's prednisone or prednisolone dose will be decreased back to the standard clinical dose of 0.75 mg/kg/day. Those subjects who had been on deflazacort may be switched back to the standard clinical dose of 0.9 mg/kg day. For either regimen, approximations of these target doses may be allowed to account for pill formulations (for prednisone and deflazacort), as in clinical practice. If either the AST or ALT exceeds >2.5X the subject's baseline values, and results are confirmed on a follow-up blood test, the prednisone or prednisolone regimen will be maintained at 1 mg/kg/day until the enzyme levels fall within a range, 2.5X the baseline value. Subjects may be asked to undergo a weekly blood test outside of prescheduled visits should the SI deem it necessary to monitor the T-cell response or AST/ALT levels more closely.

If the IFN-gamma T-cell responses show  $\geq 50$  SFC per 1 x  $10^6$  PBMCs, we may increase the dose to approximately 2 mg/kg/day depending on T-cell response measured by ELISpot assay and prolong a subsequent tapering protocol based on the individual subject's immune response profile as assessed by subsequent ELISpot assays (as on the schedule above). Based upon other studies performed at NCH, we anticipate that oral prednisone or prednisolone may be administered for up to 120 days post gene transfer prior to the return to the standard clinical corticosteroid regimen of each subject.

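### For boys enrolled under 4, functional change from baseline can reflect newly started prednisolone as well as the vector, and the plan does not separate the two

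*Combined protocol and SAP*

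**What the plan says.** Section 5.3 A sets the functional comparison as "Muscle Function at 6 and 12 months post gene transfer in comparison to baseline values". For the youngest group the synopsis words the outcome as "improvement or stabilization of Bayley-IV scores" and names no visit. Functional tests are also scheduled at Day 90 and at Months 18 and 24 (9.1.3.6, Table 8). The trial is open label, all subjects are treated, and up to three are enrolled (6.1, 6.3).

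Eligibility is "Age greater than 6 months and less than 14 years". The steroid condition in 7.1 begins "In subjects age 4 and above, stable dose and regimen of corticosteroid therapy" and asks for at least 12 weeks; there is no counterpart for younger boys. Functional baselines are taken at screening, Day -45 to Day -1 (9.1.1).

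Section 9.1.2.1 foresees the gap: "For subjects younger than 4 years of age who may not be on a corticosteroid", prednisolone is to be prescribed as immune prophylaxis, starting on Day -1. It then sends each subject back to the steroid regimen he had before treatment. Section 10.6.1 discharges all subjects on 1 mg/kg/day. If the Day 30 T-cell result is low, it says "the subject's prednisone or prednisolone dose will be decreased back to the standard clinical dose of 0.75 mg/kg/day", with no separate text for a boy who was on no steroid. It expects a course of up to 120 days and allows a prolonged taper.

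On glucocorticoids generally, 4.3.3 says that treatment has been "repeatedly shown to result in increased muscle strength and delayed loss of ambulation".

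**The concern.** A boy can serve as his own control only if his background treatment is the same at baseline and at follow-up. The 12-week rule goes some way towards that from age 4. Below 4, a boy may be tested untreated and then receive steroid and vector about one day apart. By the protocol's own account, steroid moves function in the direction that the outcome counts as success. Neither 5.3 nor Section 13 mentions steroid status, and Section 13 does not cover the functional outcomes at all.

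At stake is the interpretation of the clinical readout. With one to three subjects, one such boy could be the whole functional result. The ages concerned take in the entire Bayley-IV group (36 months or younger). They also take in half the age span of the group tested with NSAA, four-stair climb and 100MWT but not MVICT: (48 - 36)/(60 - 36) = 12/24 months.

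**Working it through.** **The plan's own figure.** The only power statement (Section 13) is a detectable SMD of 1.4 to 3.3 at 80% power for 3 to 6 subjects. For a two-sided paired t test at 0.05, power is the upper tail of a noncentral t with n - 1 degrees of freedom and noncentrality SMD × √n, beyond the 97.5% point of t. This gives 80.7% at n = 3 with SMD 3.3, and 78.1% at n = 6 with SMD 1.4. Exact 80% needs 3.26 and 1.43. The figure reproduces, but it is written for the biopsy outcomes and neither supports nor weakens this point.

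**Steroid exposure of a boy under 4 who was on none at baseline.** Inputs are the Day -1 start (9.1.2.1), the visit windows (9.1.3.6) and a course ending on Day 120 (the expectation in 10.6.1 and Table 8 footnote 5, not a cap). Month 12 is taken as Day 365, which is my assumption.

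- Time on steroid at Day 90 ± 7: 83 + 1 = 84 to 97 + 1 = 98 days
- Time off steroid at Day 180 ± 14: 166 - 120 = 46 to 194 - 120 = 74 days
- Time off steroid at Month 12 ± 14 days: 351 - 120 = 231 to 379 - 120 = 259 days

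| Functional visit | If 9.1.2.1 governs and the course ends on Day 120 | If 0.75 mg/kg/day (10.6.1) continues, or the taper is prolonged |
|---|---|---|
| Screening baseline | none | none |
| Day 90 | on steroid, 84 to 98 days after starting | on steroid |
| Day 180 | off for 46 to 74 days | on steroid |
| Month 12 | off for 231 to 259 days | on steroid at 0.75 mg/kg/day; under a taper, only if it runs that long |

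Day 90 is the one functional visit at which Table 8 itself marks steroid administration. Because the taper may begin at Day 30, this is scheduled rather than certain exposure. The synopsis names no visit, so Day 90 can be read under its criterion, although 5.3 A lists only 6 and 12 months.

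**Boys aged 4 and over.** Section 9.1.2.1 raises prednisone or prednisolone to 1.0 mg/kg/day. From the standard 0.75 that is an increase of 0.25 mg/kg/day, or one third, against an increase from zero to 1.0 for an untreated boy. Boys on deflazacort change drug. Their exposure can therefore also rise after baseline, by less.

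**Size of the effect.** The documents give no steroid effect on any functional scale and none for infants or for Bayley-IV, so a magnitude cannot be derived from them.

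**The case against.** The strongest reply is that the steroid will be gone by the visits that 5.3 A names. Section 9.1.2.1 returns each boy to his earlier regimen. Section 9.1.3.4 schedules a blood draw two weeks after the prednisone dose is back at baseline. Table 8 places that draw between Day 120 and Day 150 and ends its steroid row at Day 120. The wording in 10.6.1 presupposes a boy who was already on 0.75 mg/kg/day, and its closing sentence refers to each subject's own regimen. Section 4.3.3 describes the effect of treatment, not its persistence after stopping.

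Much of this stands. A reader might infer that the 6- and 12-month comparisons necessarily set an untreated baseline against a boy taking steroid plus vector. The documents do not support that: it follows only if the 0.75 mg/kg/day text applies to him or the taper is prolonged. Otherwise carry-over is what remains. But 10.6.1 has no text for a boy on no steroid, its 120 days is an expectation, and Day 90 is unaffected by the reply.

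It is also fair that function is exploratory, that safety is primary, and that no sentence in the plan assigns functional change to the vector; that attribution is what a reader would supply. Finally, normal development in boys under 4 is a competing explanation. It adds to the difficulty of reading raw change and does not remove the steroid problem.

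**Conclusion.** The point holds as a matter of interpretation. For a boy under 4 who is off steroid at baseline, change in Bayley-IV, NSAA, four-stair climb or 100MWT can reflect steroid as well as vector. The confounding is clearest at Day 90. At 6 and 12 months it is direct or limited to possible carry-over, depending on two passages that conflict for such a boy. Boys aged 4 and over share a smaller version.

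Two stronger inferences should be avoided. One is a numerical inflation. If one assumes a steroid shift of 0, 0.5, 1 or 2 SD of the change score, no vector effect, no growth or disease trend and a normal distribution, the chance that one boy does not decline is 50%, 69%, 84% or 98%. These figures only restate the assumed shift, and zero growth is not tenable for boys from 6 months of age. The other is that boys aged 4 and over are fully protected by the 12-week rule; their dose may also rise after baseline.

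The conclusion assumes that at least one boy under 4 and off steroid is enrolled, which the plan permits but does not predict. Severity is modest: it affects exploratory outcomes and leaves the primary safety outcome untouched.

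**What to change.** In 5.3 A and the synopsis:

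1. List the steroid drug and mg/kg/day beside every functional score, including baseline, with the prophylactic course included. Concomitant medication and weight are already collected at these visits.
2. For a boy not on corticosteroid at his baseline functional test, label change from baseline at any visit where he is on steroid as the combined effect of steroid and vector. Do not count it as vector-related improvement or stabilization. At visits after steroid has stopped, report the change with the time since the last dose and a carry-over caveat.
3. Reconcile 9.1.2.1 with 10.6.1 on what follows prophylaxis for a boy who was on no steroid. No regimen is proposed here.

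The trigger in item 2 is deliberately steroid status at the baseline test. Requiring 12 weeks of stable steroid before that test would also catch eligible boys aged 4 and over: 7.1 counts the 12 weeks back from gene transfer, so a Day -45 baseline may have only 84 - 45 = 39 days behind it. Likewise, item 2 looks at exposure at each visit, because excluding every boy whose exposure has ever differed since baseline would bar him at all later visits.

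The cost is a few sentences, with no new data, visits or subjects. The downside is that fewer visits can support a functional claim attributed to the vector.
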